9.3.3 Electrocardiograms

The ECGs will be recorded digitally at the sites by using the standard 12-leads as outlined in [Table 2](#), [Table 3](#), [Table 5](#), [Table 6](#), [Table 10](#), [Table 11](#), and [Table 15](#). ECGs will be performed in accordance with the ECG manual issued by the vendor. The digital ECGs will be transmitted from the sites electronically to a central laboratory for a measurement of the cardiac intervals and morphologic assessment by a central cardiologist.

An overall interpretation of the ECGs will be performed by the investigator, or the investigator may delegate this task to a cardiologist, if applicable. The investigator ECG interpretation must be done using the paper ECG reading from the ECG machine by signing and dating the print out. In case of discrepancy between central and the investigator ECG readings, the central reading will be used for trial analysis purposes.

For the ECG recordings, the subjects must be resting and in a supine or reclined position for at least 10 minutes. ECGs should be done in triplicate, 5 minutes apart (\pm 5 minutes). In case any

irregularity (eg, vomiting or cough) occurs during the recording of the ECG, the ECG should be repeated.

9.3.4 ECOG Performance Status

The ECOG performance status will be assessed by the investigator as indicated in [Table 2](#), [Table 3](#), [Table 5](#), [Table 6](#), [Table 10](#), [Table 11](#), and [Table 15](#). Performance status will be scored using the ECOG performance status scale index (refer to [Appendix 11](#)).

9.3.5 Constitutional Symptoms (B Symptoms)

Constitutional symptoms will be evaluated at screening and before GEN3009 administration as indicated in [Table 2](#), [Table 3](#), [Table 5](#), [Table 6](#), [Table 10](#), [Table 11](#), and [Table 15](#). Constitutional symptoms include night sweats, weight loss > 10% over 6 months, and extreme fatigue and/or fever without infection.

9.3.6 Survival Status

Survival status will be assessed every 3 months via telephone contact, email, or on-site visit, after the last administration of GEN3009 and/or GEN3013 and will continue until the subject dies or withdraws from the trial. Data will be collected as reported by the subject regarding disease status, new anti-lymphoma treatment, any other malignancy other than the disease under study (ie, a second primary malignancy), and survival status, if available. If the subject is not available for this assessment, the response should be entered as “lost to follow up” ([Section 8.4](#)).

9.4 Clinical Laboratory Assessments

9.4.1 Laboratory Parameters

The laboratory parameters listed in [Table 31](#) must be performed as indicated in the visit assessment schedules (refer to [Table 2](#), [Table 3](#), [Table 5](#), [Table 6](#), [Table 10](#), [Table 11](#), and [Table 15](#)). Any local or central laboratory values leading to a dose modification/delay should be recorded as an AE ([Section 10.2.5](#)).

Laboratory abnormalities are to be recorded as AEs also if considered clinically relevant by the investigator (see [Section 10.2.5](#)).

Local Laboratory Assessments

Local laboratory values for hematology, biochemistry and coagulation must be obtained within 3 days prior to the first dose of each subject and reviewed by the investigator prior to the first dose to ensure that the subject is still eligible. For the subsequent doses, these laboratory values must be obtained within 1 day, preferably on the same day prior to each GEN3009 and/or GEN3013 administration, and reviewed by the investigator prior to each administration to ensure the subject can be dosed in line with the dosing instructions as defined in the protocol. As this is a FIH trial, the timing of safety laboratory assessments may be adjusted during the trial based on emerging data.

Additional local laboratory values may be obtained at the discretion of the investigator and used for other clinical treatment decisions of the subject.

Local laboratory assessments outlined in [Table 31](#) must be recorded.

Central Laboratory Assessments

Central laboratory assessments include immunophenotyping for lymphocytes (Section 9.8.3.1), PK (Section 9.5), immunogenicity assessments (ADAs) (Section 9.6), and cytokine measurements (Section 9.8.3.2). Additional biopsy and blood samples for exploratory biomarker analyses will be collected (refer to Sections 9.8.2 and 9.8.3) and shipped for centralized testing.

Table 31 Protocol-Required Laboratory Assessments

Local Laboratory Assessments	
Test Category	Test Name
Hematology	Hemoglobin, hematocrit, white blood cells including differential (neutrophils, basophils, eosinophils, lymphocytes [both percent and absolute]), monocytes (absolute values for differential are preferred), reticulocytes and platelets. Reporting the proportion of prolymphocytes is desirable when these are present.
Quantitative lymphocyte subsets	B cells, T cells, and NK cells (both absolute and percent)
Biochemistry	Albumin, alkaline phosphatase, alanine aminotransferase (ALT), aspartate aminotransferase (AST), bicarbonate, lactate dehydrogenase (LDH), calcium, chloride, magnesium, inorganic phosphorus (phosphate), sodium, potassium, creatinine, total bilirubin, blood urea nitrogen (BUN) or urea, uric acid, glucose (non-fasting), total protein, C-reactive protein (CRP), D-dimer, ferritin. Tumor lysis sample includes uric acid, potassium, inorganic phosphorus (phosphate), calcium and creatinine.
Coagulation	Prothrombin time (PT), international normalized ratio (INR), activated partial thromboplastin time (APTT), fibrinogen
Serology	Hepatitis B surface antigen (HBsAg) and hepatitis B core antibody (HBcAb). If positive serology, PCR for HBV-DNA to be performed. Hepatitis C virus (HCV) antibody. If positive serology PCR for HCV RNA to be performed. Cytomegalovirus (CMV) serology (IgG and IgM) at screening. If positive, further surveillance, ie, PCR for CMV-DNA to be performed at the investigator's discretion. Note: HIV testing is required at screening only if required per local health authorities or institutional standards. .
Additional tests	Beta2-microglobulin (at screening only). Immunoglobulins: IgA, IgG and IgM (at screening, at start of each cycle, and at the treatment discontinuation visit).
Urinalysis	pH, glucose, protein, blood, ketones, bilirubin, urobilinogen, nitrite, leukocyte esterase, specific gravity.
Pregnancy test	For female subjects with childbearing potential, a serum pregnancy test (beta-hCG) must be performed at screening; urine OR serum pregnancy test must be performed at the start of each cycle, at the treatment discontinuation visit, and safety follow up visit.
DLBCL or CLL	For subjects with DLBCL, major biologically distinct molecular subtypes (germinal center B-cell (GCB) and activated B-cell [ABC]), MYC positivity (IHC and FISH data), chromosomal rearrangements of MYC plus BCL2 (double-hit lymphoma) and overexpression of MYC and BCL2 proteins (double-expressor lymphoma) will be collected. For subjects with CLL/SLL, FISH data for del(13q), del(11q), del(17p), and DNA sequencing for TP53 andIGHV mutational status will be collected.
Bone marrow biopsy and/or aspirate	For subject response assessments, perform locally.

Central Laboratory Assessments/Specialty Laboratories	
Test Category	Test Name
Immunophenotyping	Absolute blood cell counts leukocytes such as B cells, NK cells, monocytes and T cells; immune cell functional and activation markers (eg, CD69, CD25, CD86, CD16, CD32), target (CD37, CD3, CD20) and mCRP expression on leukocytes (Section 9.8.3.1)
PK	Plasma levels of GEN3009 and GEN3013
Cytokines	Plasma or serum levels of cytokines CCI (Section 9.8.3.2)
Immunogenicity	Serum presence of antibodies against GEN3009 and/or GEN3013 (ADAs)
Complement	CH50 measurements in serum (Section 9.8.3.3)
Protein expression analysis	CD37 protein expression in tumor biopsies during dose escalation CD37, CD59, CD68/CD163, CD56, CD20 expression in tumor biopsies during expansion CD37, CD3, CD68/CD163, CD56, CD20 expression in tumor biopsies during expansion for combination GEN3009 + GEN3013 (Section 9.8.2.1)
BCR sequencing (MRD assessment)	Quantification of malignant B-cell DNA in peripheral blood to detect MRD (Section 9.2.2.3)
Saliva DNA	Genomic DNA control for tumor DNA sequencing (Sections 9.8.3.4)
DNA/RNA and ctDNA sequencing	Mutational and gene expression profiling in tumor and/or plasma (Sections 9.8.2.2 , 9.8.2.3 , and 9.8.3.4)

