g. Samples to be taken C5, C7, C10 and C13 only. After C13 a sample will be obtained every 6 months (± 1 month) for up to 3 years.

h. Sample to be taken during Safety Run-in only.

i. Only in case of full infusion of GEN3009 on Day 1

j. Only in case of GEN3009 split dose between Day 1 and Day 2

Table 14 Visit Assessment Schedule for MRD – Expansion GEN3009 + GEN3013

Cycle	Cycles 1, 2, 3, 5, 7, and 10	Cycle 13 and onward
Day or Time post dose (window)	Day 1 (+2 days)	Day 1 (+2 days)
Whole blood MRD ^a	X	A whole blood sample will be obtained every 6 months (± 1 month) for up to 3 years
Bone marrow aspirate MRD	
For B-cell NHL subjects with bone marrow involvement at baseline: If a subject is in CR by FDG-PET, a portion of the aspirate collected to confirm CR will be used to assess MRD.For B-cell NHL subjects with no bone marrow involvement at baseline, no bone marrow examination for MRD is required.If a subject is MRD-positive in the bone marrow but maintains CR, an additional bone marrow aspirate will be collected after 3 months, if clinically feasible.	

a. Upon reaching CR on PET-CT scan, an additional blood sample will be collected if not within 2 weeks of another collection to evaluate MRD.

Table 15 GEN3013 Repriming Cycle – Expansion GEN3009 + GEN3013 (including Safety Run-in)

	Day 1	Day 8	Day 15	Day 22
Body Weight	X		X	
Complete physical examination	X			
Lymph node examination	X			
Neurological Evaluation (ICANS) ^b	X	X	X	X
Vital signs ^c	X	X	X	X
12-Lead ECG (triplicate)	X			
ECOG Performance Status	X			
Constitutional Symptoms (ie, B Symptoms)	X		X	
Adverse Events	X	X	X	X
Previous and concomitant medications	X	X	X	X
Concomitant procedures	X	X	X	X
STUDY TREATMENT ADMINISTRATION				
Hospitalization ^d			X	
Premedications ^e	X	X	X	X
CRS prophylaxis ^f	X	X	X	X
GEN3013 administration	X	X	X	X
LOCAL LABORATORY ASSESSMENTS				
Hematology	X		X	
Biochemistry	X		X	
Coagulation	X		X	
Immunoglobulins (IgA, IgE, IgG, gM)	X			
Urinalysis	X			
Pregnancy Test (urine or serum) ^g	X			
TLS Monitoring			X	
CENTRAL LABORATORY ASSESSMENTS				
Immunophenotyping (by flow cytometry)	X ^h	X ^h	X ^h	X
Pharmacokinetics (GEN3009 and GEN3013)	X ^h	X ^{h,i}	X ^{h,i}	X ^{h,i}
Anti-drug antibodies	X ^h			

- a. Once the full repriming cycle is completed, the subject should resume treatment with Day 1 of the next planned cycle (subsequent to the cycle during which the dosing was delayed); see Section 7.4.2.2.

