7.4.2.2 GEN3013 Dose Modification Rules

Dose reduction is not allowed for GEN3013 on an individual subject level in this trial. Refer to Section [4.3](#) for dosing rationale.

If a dose is delayed more than 6 weeks, the subject should be asked to perform an unscheduled visit for collection of AEs, concomitant medications, laboratory values (including hematology, biochemistry, and coagulation values), and a limited physical examination (as clinically indicated) after consultation with the sponsor's medical monitor.

A repriming cycle is necessary if dose is delayed at certain time points, as described below. A repriming cycle consists of a weekly schedule of a priming dose, intermediate dose, and 2 full doses. Refer to [Table 15](#) for the repriming cycle Visit Assessment Schedule.

A repriming cycle should occur:

- For the second GEN3013 full dose onward (ie, C2D1), if the interval between the previous dose of GEN3013 and next planned dose exceeds 6 weeks.

During the repriming cycle, CRS prophylaxis must be resumed with 3 consecutive days of corticosteroids beginning at each GEN3013 dose, until at least 1 full dose of GEN3013 is administered without subsequent occurrence of CRS Grade ≥ 2 (see Section [6.2.2](#)).

Once the full repriming cycle is completed, the subject should resume treatment with Day 1 of the next planned cycle (subsequent to the cycle during which the dosing was delayed). For example, if the subject experiences a 7-week delay after C3D1, the subject should receive a repriming cycle, then continue treatment at C4D1. GEN3009 dose will continue as scheduled.

If GEN3013 dose is delayed, withheld, or discontinued during the combination treatment period, GEN3009 can be continued if approved by the sponsor's medical monitor.

Refer to Section [7.4.3](#) for information about dose modifications due to AEs.

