7.4.3.1 Cytopenias (All Cohorts)

GEN3009 and/or GEN3013 dose (regardless of being monotherapy or combination therapy) will be held for up to 4 weeks for the following hematologic laboratory results:

Table 25 Dose Modification Rules for Cytopenias

Laboratory Parameter	Laboratory Value	
	Hold GEN3009 and/or GEN3013 Dose	Resume GEN3009 and/or GEN3013 Dose
Platelet count ^a	<50 × 10 ⁹ /L	≥50 × 10 ⁹ /L
Neutrophil count	<0.5 × 10 ⁹ /L	≥0.5 × 10 ⁹ /L
Hemoglobin	<8 g/dL (<5 mmol/L)	≥8 g/dL (>5 mmol/L)

No dose-reduction is allowed for GEN3009 or GEN3013, but a repriming cycle may be needed if the interval between the previous dose of GEN3013 and next planned dose exceeds 6 weeks.

a. In subjects with CLL having platelets ≥30×10⁹/L (30,000/µL) can be dosed after the consultation with the sponsor's medical monitor.

Note: If the investigator deems any of the above cytopenias are secondary to bone marrow involvement by the disease, continuation of study treatment can be discussed with the sponsor's medical monitor. Transfusion with blood products (eg, RBC, platelets) and/or administration with G-CSF is permitted if needed. G-CSF must be used in case of ≥Grade 3 neutropenia during Dose Escalation and safety run in parts of the study. See Sections 6.6.1 and 7.5.1.

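### The repriming schedule (Table 15) marks safety bloods for 2 of 4 GEN3013 doses, while Section 9.4.1 requires them before every dose; the passages need reconciling

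*Protocol*

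**What the plan says.** Protocol Section 9.4.1 sets the pre-dose laboratory rule. It first names the three panels: "Local laboratory values for hematology, biochemistry and coagulation must be obtained within 3 days prior to the first dose of each subject". For later doses, "these laboratory values must be obtained within 1 day, preferably on the same day prior to each GEN3009 and/or GEN3013 administration", and they are to be "reviewed by the investigator prior to each administration to ensure the subject can be dosed in line with the dosing instructions". The opening of the same section says that the listed laboratory parameters "must be performed as indicated in the visit assessment schedules", and Table 15 is among the schedules it names.

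Table 15 (Section 1) is the visit schedule for a GEN3013 repriming cycle. Its dosing row reads "GEN3013 administration X X X X", under Days 1, 8, 15 and 22. Section 7.4.2.2 agrees: "A repriming cycle consists of a weekly schedule of a priming dose, intermediate dose, and 2 full doses". In the local laboratory block, the hematology, biochemistry and coagulation rows each carry marks on Days 1 and 15 and nothing on Days 8 and 22.

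Section 7.4.3.1 (Table 25) makes dosing depend on blood counts. GEN3009 and/or GEN3013 "will be held for up to 4 weeks for the following hematologic laboratory results", namely platelets, neutrophils and hemoglobin.

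The regular combination schedules (Tables 10 and 11) mark all three panels on every GEN3013 dosing day, and their footnotes refer the reader to Section 9.4.1 for laboratory timing. Table 15 has no such footnote.

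**The concern.** Section 9.4.1 contains two mandatory instructions that disagree for the repriming cycle: test before every administration, and test as the schedule indicates. Sites usually plan visits from the schedule table. One that does so here would draw no safety bloods for the intermediate dose (Day 8) or the second full dose (Day 22).

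The subjects affected are those whose GEN3013 gap exceeded 6 weeks. Table 25 itself notes that a cytopenia hold may lead to repriming, so subjects recovering from low counts are a foreseeable part of this group. Section 7.4.2.2 says GEN3009 continues as scheduled during repriming, and Section 2.1.4.1 reports neutropenia in 94.4%, thrombocytopenia in 38.9% and anemia in 27.8% of the 18 subjects treated with GEN3009 so far.

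A current count is what Table 25 acts on. Laboratory changes are also a primary endpoint of the combination safety run-in (Table 19) and a secondary endpoint of the combination DLBCL expansion (Table 20), so thinner sampling bears on the safety data as well.

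**Working it through.** The protocol states no figure to reproduce. The check sets the Table 15 dosing row against its laboratory rows and tests each dose against the 1-day window in Section 9.4.1.

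**Column reading.** Table 15 places its hospitalization mark under Day 15. Footnote d ties hospitalization to the third (full) dose, which is the Day 15 dose. The columns are therefore read correctly and the empty cells are not an extraction fault.

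**Dose by dose.** Days since last marked sample = dosing day minus the latest marked laboratory day.

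| Repriming day | GEN3013 dose | Three panels marked in Table 15 | Days since last marked sample | Within 1 day |
|---|---|---|---|---|
| 1 | Priming | Yes | 1 − 1 = 0 | Yes |
| 8 | Intermediate | No | 8 − 1 = 7 | No |
| 15 | First full | Yes | 15 − 15 = 0 | Yes |
| 22 | Second full | No | 22 − 15 = 7 | No |

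Doses without a scheduled sample inside the window: 4 − 2 = 2 of 4.

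**Do other Table 15 samples fill the gap?** No.
- Blood is drawn on Days 8 and 22 for PK and immunophenotyping, but these are central laboratory tests. Table 31 describes immunophenotyping as leukocyte counts and markers, without platelets or hemoglobin.
- TLS monitoring is marked on Day 15 only.
- The unscheduled visit in Section 7.4.2.2 for a delay of more than 6 weeks is not tied to Days 8 or 22.

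**Could Table 11 supply the missing days?** Only in part. Table 11 marks all three panels on Days 1, 8, 15 and 22 of Cycles 2 and 3, while GEN3009 is weekly. From Cycle 4 it marks Day 1 only.

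Where a cytopenia hold would lead to repriming depends on the usual dosing interval. Assume the hold stays within the 4-week limit and is counted from the planned dose date:
- Weekly dosing: 1 + 4 = 5 weeks at most, which does not exceed 6.
- Four-weekly dosing: 4 + 4 = 8 weeks at most, and 6 weeks is exceeded once the hold passes 6 − 4 = 2 weeks.

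Under that assumption, repriming after a cytopenia hold arises in the four-weekly phase, where Table 11 offers no Day 8 or Day 22 laboratory marks. Longer delays in Cycles 2 and 3 can also lead to repriming (Section 7.4.2.2 gives a 7-week example after Cycle 3 Day 1), and there the overlap could help.

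**Which rule needs which panel?** Table 25 uses hematology values only. Biochemistry and coagulation on Days 8 and 22 rest on Section 9.4.1 alone.

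**The case against.** The strongest reply is that the requirement is already in the protocol. A repriming dose is a GEN3013 administration, so Section 9.4.1 covers Days 8 and 22 whatever Table 15 marks. It also allows extra local tests at the investigator's discretion and changes of timing on emerging data. This largely stands. A reader might infer from Table 15 that the pre-dose check has been removed and that the hold rule cannot be applied on those days; the documents do not support that. What remains is that the same section also sends sites to Table 15, that Table 15 lacks the cross-reference found in Tables 10 and 11, and that no emerging data are cited to justify a lighter repriming schedule.

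A second reply is that Table 15 may not be the subject's whole schedule. It has no GEN3009 dosing row, yet GEN3009 continues, and footnote i anticipates weekly GEN3009. In that phase the Table 11 laboratory days may run alongside. This stands as a qualification: 2 of 4 counts marks in one table and does not show that half of repriming doses would be given without a count. But the protocol does not state the overlap, and it does not help from Cycle 4.

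A third reply concerns safety data. A reader might infer that cytopenias between the marked samples would go unrecorded. That is too strong. Adverse events are marked on all four days of Table 15, Section 7.5.1 calls for counts to be followed until recovery, and hematology is marked again on Day 1 of the next cycle. A new, asymptomatic cytopenia that resolves between samples is the kind most likely to be missed.

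**Conclusion.** The inconsistency is real and sits on the face of the protocol. Table 15 schedules the three panels for 2 of 4 GEN3013 doses, and the other two doses, one intermediate and one full, fall 7 days after the last scheduled sample, against a 1-day rule. For a site that follows Table 15 alone, Table 25 would lack a current scheduled platelet, neutrophil or hemoglobin value on Days 8 and 22, and some cytopenias could be missed.

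This is a conflict between schedule and text. It is not evidence that the pre-dose check is absent or that the hold rule is unworkable, because Section 9.4.1 still binds sites. The size of the effect depends on how many sites work from Table 15 alone and how many subjects reprime; the documents give neither. No effect on the descriptive laboratory endpoints is shown. The point is worth correcting because it concerns pre-dose safety checks in subjects returning after a long gap and is cheap to settle.

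**What to change.** Reconcile the laboratory rows of Table 15 with Section 9.4.1 and Table 25, so that the repriming schedule and the pre-dose laboratory rule agree for every marked GEN3013 dosing day, including Days 8 and 22. State whether the Table 11 laboratory days also apply during a repriming cycle, and add to Table 15 the kind of reference to Section 9.4.1 that Tables 10 and 11 carry. Which passage prevails is for the sponsor to decide; whichever does, the others should be brought into line with it.

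The cost is a table or text correction. If Section 9.4.1 stands, it adds at most two local blood draws per repriming cycle, at visits that already include blood sampling. Doses and hold thresholds are not affected.

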9.5 Pharmacokinetics

Venous blood samples of approximately 4 mL will be collected for measurement of plasma concentrations of GEN3009 or GEN3013 as specified in [Table 4](#) (Dose Escalation), [Table 7](#) (Expansion Monotherapy) or [Table 12](#) (Expansion Combination). Additional samples may be collected during the trial if warranted and agreed upon between investigator and sponsor, eg, for safety monitoring. Instructions for the collection and handling of biological samples will be provided by the sponsor in the laboratory manual.

Samples collected for analyses of GEN3009 or GEN3013 plasma concentration may additionally be used to evaluate safety or efficacy aspects that address concerns arising during or after the trial period. Genetic analyses will not be performed on these plasma samples. Subject confidentiality will be maintained.

Plasma samples will be analyzed to determine concentrations of GEN3009 or GEN3013. Validated, specific, and sensitive ligand binding assays/immunoassays will be used under the supervision of the sponsor at an assay CRO.

9.6 Immunogenicity

Venous blood samples will be collected for measurement of serum concentrations of ADAs as specified in [Table 4](#) (Dose Escalation), [Table 7](#) (Expansion), or [Table 12](#) (Expansion Combination). In the Expansion Combination cohort, 1 sample each for GEN3009 and GEN3013 are to be drawn.

Samples should also be collected at the final visit from subjects who discontinued trial drug or were withdrawn from the trial. At visits where ADAs will be evaluated, 1 blood draw of sufficient volume can be used.

Each serum sample for ADA evaluation will be divided into 2 aliquots (one for ADA analysis and a back-up). Plasma concentrations of GEN3009 or GEN3013 will be analyzed (refer to Section 9.5) and those data will be used for interpretation of the ADA data.

The ADA samples may additionally be used to evaluate safety or efficacy aspects that address concerns arising during or after the trial period for further characterization of immunogenicity.

Samples may be stored according to local regulations at a facility selected by the sponsor to enable further analysis of immune responses to GEN3009 or GEN3013.

Genetic analyses will not be performed on these serum samples. Subject confidentiality will be maintained.

The detection and titer characterization of ADAs will be performed using validated, specific and sensitive Electrochemiluminescence Immunoassay (ECLIA) methods and the titer of confirmed positive samples will be reported. The analysis will be performed under the supervision of the sponsor at an assay CRO. Neutralization characterization of ADAs will be performed at sponsor laboratories using appropriate methods.

